9.5.1.5.1 ADVERSE EVENTS AND EVENTS ASSOCIATED WITH SPECIAL SITUATIONS

An AE is any untoward medical occurrence in a subject or clinical investigation subject administered an investigational product. An AE does not necessarily have a causal relationship with the medicinal product. For this study, the study drug is elenbecestat (E2609).

The criteria for identifying AEs in this study are:

- Any unfavorable and unintended sign (including an abnormal laboratory finding), symptom, or disease temporally associated with the use of an investigational product, whether or not considered related to the investigational product (Note: Every sign or symptom should not be listed as a separate AE if the applicable disease [diagnosis] is being reported as an AE)
- Any new disease or exacerbation of an existing disease
- Any deterioration in nonprotocol-required measurements of a laboratory value or other clinical test (eg, ECG or x-ray) that results in symptoms, a change in treatment, or discontinuation of study drug
- Recurrence of an intermittent medical condition (eg, headache) not present pretreatment (Baseline)
- An abnormal laboratory test result should be considered an AE if the identified laboratory abnormality leads to any type of intervention, withdrawal of study drug, or withholding of study drug, whether prescribed in the protocol or not.

All AEs observed during the study will be reported on the eCRF. All AEs, regardless of relationship to study drug or procedure, should be collected beginning from the time the subject signs the study ICF through the last visit (Visit 15, as shown in [Table 3](#)). Subjects who fail screening primarily due to AE(s) must have the AE(s) leading to screen failure reported on the Screening Disposition eCRF and the Adverse Event eCRF. SAEs will be collected for 12 weeks after the last dose.

Abnormal laboratory values should not be listed as separate AEs if they are considered to be part of the clinical syndrome that is being reported as an AE. It is the responsibility of the investigator to review all laboratory findings in all subjects and determine if they constitute an AE. Medical and scientific judgment should be exercised in deciding whether an isolated laboratory abnormality should be classified as an AE. Any laboratory abnormality considered to constitute an AE should be reported on the Adverse Event eCRF.

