9.5.4.1 Reporting of Serious Adverse Events

All SAEs, regardless of their relationship to study treatment, must be reported on a completed SAE form by email or fax as soon as possible but no later than 24 hours from when the investigator becomes aware of the event.

SAEs, regardless of causality assessment, must be collected up to 12 weeks after the last dose of study drug. All SAEs must be followed to resolution or, if resolution is unlikely, to stabilization. Any SAE judged by the investigator to be related to the study treatment or any protocol-required procedure should be reported to the sponsor regardless of the length of time that has passed since study completion.

The detailed contact information for reporting of SAEs is provided in the Investigator Study File.

For urgent safety issues, please ensure all appropriate medical care is administered to the subject and contact the appropriate study team member listed in the Investigator Study File.

It is very important that the SAE report form be filled out as completely as possible at the time of the initial report. This includes the investigator's assessment of causality.

Any follow-up information received on SAEs should be forwarded within 1 business day of its receipt. If the follow-up information changes the investigator's assessment of causality, this should also be noted on the follow-up SAE form.

Preliminary SAE reports should be followed as soon as possible by detailed descriptions including copies of hospital case reports, autopsy reports, and other documents requested by the sponsor.

The investigator must notify his/her IRB/IEC of the occurrence of the SAE in writing, if required by their institution. A copy of this communication must be forwarded to the sponsor, or its designee, to be filed in the sponsor's Trial Master File.

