9.5.5 Completion/Discontinuation of Subjects

A subject may elect to withdraw from the study at any time for any reason. All subjects who discontinue study drug early for any reason will undergo an ED Visit within 7 days of their

last dose of study drug (see [Section 9.1.2.2](#)). In addition, Follow-Up Visits will be scheduled 4 and 12 weeks after the last dose of study drug (Visit 14 and Visit 15, respectively) (see [Section 9.1.2.2](#)). These Follow-Up Visits will be conducted to monitor efficacy and safety parameters after early withdrawal from the study or discontinuation of study drug. See [Table 3](#) for full details of the assessments to be performed at these visits.

All subjects who discontinue study drug before reaching 12 months of treatment will also be asked to return to the clinic for a 12 month clinical assessment and then again at 24 months. Subjects who discontinued treatment between 12 and 24 months of treatment will be asked to return to the clinic for a 24 month clinical assessment. Subjects who discontinue early from study drug are considered “on study” as long as they continue to return for their clinical assessments at 12 and 24 months as outlined above, at which efficacy and quality of life will be assessed along with concomitant medications and AEs. However, subjects who discontinue study drug early are not considered to have ‘completed’ the study as a final Subject Disposition. A subject removed from the study for any reason may not be replaced.

The investigator will promptly explain to the subject involved that the study will be discontinued for that subject and provide appropriate medical treatment and other necessary measures for the subject. A subject who has ceased to return for visits will be followed up by mail, phone, or other means to gather information such as the reason for failure to return, the status of treatment compliance, the presence or absence of AEs, and clinical courses of signs and symptoms.

The primary reasons for early withdrawal from the study are: AE, lost to follow-up, subject choice, withdrawal of consent, pregnancy, study terminated by sponsor, and other. The secondary reasons for early withdrawal from the study are: AE, subject choice, and other.

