9.7.1.8.2 ADVERSE EVENTS

The AE verbatim descriptions (investigator terms from the eCRF) will be classified into standardized medical terminology using the Medical Dictionary for Regulatory Activities (MedDRA). AEs will be coded to the MedDRA (Version 19.0 or higher) lower level term closest to the verbatim term. The linked MedDRA PT and primary system organ class (SOC) are also captured in the database.

A TEAE is defined as:

- An AE that emerges during treatment within 4 weeks of the last dose of study drug, having been absent at pretreatment (Baseline) or
- Reemerges during treatment, having been present at pretreatment (Baseline) but stopped before treatment, or
- Worsens in severity during treatment relative to the pretreatment state, when the AE is continuous.

Only those AEs that are treatment-emergent will be included in summary tables. All AEs, treatment-emergent or otherwise, will be presented in subject data listings.

The TEAEs will be summarized by treatment group on the Safety Analysis Set. The incidence of TEAEs will be reported as the number (percentage) of subjects with TEAEs by SOC and PT. A subject will be counted only once within an SOC and PT, even if the subject experienced more than 1 TEAE within a specific SOC and PT. The number (percentage) of subjects with TEAEs will also be summarized by maximum severity (mild, moderate, or severe). The number (percentage) of subjects with TEAEs will also be summarized by relationship to study drug (Yes [related] and No [not related]).

The number (percentage) of subjects with treatment-related TEAEs will be summarized by SOC and PT. Treatment-related TEAEs include those events considered by the investigator to be related to study drug. The number (percentage) of subjects with treatment-related TEAEs will also be summarized by maximum severity (mild, moderate, or severe).

AEs will be summarized by the following subgroups: region, , prior treatment with AChEIs or memantine (no or yes), and clinical subpopulation (MCI due to AD or the early stages of AD). (revised per Amendment 01)

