The number (percentage) of subjects with TEAEs leading to death will be summarized by MedDRA SOC and PT for each treatment group. A subject data listing of all AEs leading to death will be provided. The number (percentage) of subjects with treatment-emergent SAEs will be summarized by MedDRA SOC and PT for each treatment group. A subject data listing of all SAEs will be provided. The number (percentage) of subjects with TEAEs leading to discontinuation from study drug will be summarized by MedDRA SOC and PT for each treatment group. A subject data listing of all AEs leading to discontinuation from study drug will be provided.

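### Serious and fatal adverse events starting 4 to 12 weeks after the last dose must be collected but enter no by-arm SAE or fatal-AE table

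*Protocol*

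**What the plan says.** Section 9.7.1.8.2 defines a new treatment-emergent event as "An AE that emerges during treatment within 4 weeks of the last dose of study drug", provided it was absent at baseline. It then sets the rule for display: "Only those AEs that are treatment-emergent will be included in summary tables". Everything else goes to subject data listings.

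The two tables that matter most repeat the limit. For deaths: "The number (percentage) of subjects with TEAEs leading to death will be summarized by MedDRA SOC and PT for each treatment group". For serious events: "The number (percentage) of subjects with treatment-emergent SAEs will be summarized by MedDRA SOC and PT for each treatment group". The tables of treatment-related events in the same section are also built on TEAEs. Full listings of SAEs and of AEs leading to death are promised.

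Collection runs longer. Section 9.5.1.5.1 says that AEs "should be collected beginning from the time the subject signs the study ICF through the last visit", which is Visit 15, and that "SAEs will be collected for 12 weeks after the last dose". Section 9.5.4.1 repeats the duty: "SAEs, regardless of causality assessment, must be collected up to 12 weeks after the last dose of study drug". It adds that a drug-related SAE is reportable however late it is found. For subjects who stop drug early, section 9.5.5 adds visits at months 12 and 24 "at which efficacy and quality of life will be assessed along with concomitant medications and AEs".

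**The concern.** The collection window after the last dose is three times as long as the tabulation window. The sponsor asks sites to record serious events through week 12 off drug and then bars those with onset after week 4 from every by-arm AE table. The bar covers an SAE in, say, week 6 that the investigator judges drug-related.

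This is a written restriction, not a detail left open for the SAP. Under this text, an SAP table of all SAEs by system organ class and preferred term would conflict with the protocol.

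At stake is the completeness of the serious-harm comparison in a 24-month trial of people aged 50 to 85. The protocol itself watches for immune effects: section 7.1 describes lymphocyte reductions and relapse of oral herpes. A reader who wanted all SAEs or all fatal AEs by arm would have to count them from listings.

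**Working it through.** The protocol gives no figure for this gap, so there is none to reproduce. The point rests on comparing windows; the arithmetic only sizes it.

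**Windows, in weeks after the last dose**

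| Item | Ends at | Source |
|---|---|---|
| New event counts as a TEAE | 4 | 9.7.1.8.2 |
| Fatal-AE and SAE tables by arm | 4 (TEAEs only) | 9.7.1.8.2 |
| SAE collection, any causality | 12 | 9.5.1.5.1, 9.5.4.1 |
| AE collection (Visit 15) | 12 | 9.5.1.5.1, Table 3 |

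Collected but not tabulated: 12 − 4 = 8 weeks, or 8/12 = 67% of the mandated post-dose period. For a completer, the last dose is at week 104, the tables close at 104 + 4 = week 108, and collection closes at 104 + 12 = week 116.

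**Does another planned by-arm table cover these events?**
- Section 9.7.1.8 says in general that AE incidence is summarized by treatment group. The specific TEAE rule in 9.7.1.8.2 governs how that is done.
- Section 9.7.1.3 tabulates reasons for study withdrawal by arm, and AE is one of them. A late serious or fatal event that ends participation could be counted there, but without seriousness, organ class or preferred term. Death is not a listed reason.
- Section 9.7.1.8.3 summarizes laboratory values at each postbaseline visit, so laboratory findings off drug are covered. A clinical event such as a serious infection is not.
- Section 9.7.3 has the DSMB review cumulative safety data, but no study table follows from that.

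No planned by-arm table shows these events as SAEs or as fatal AEs.

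**Person-time in the gap**

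Inputs: 665 subjects per arm and 30% dropout (9.7.2), and 52.18 weeks per year. The 665 is sound. With a difference of 0.25 × 1.75 = 0.4375 and SD 2.05, the requirement is 462 per arm before dropout and 462/0.7 = 660 after it (662 using the t-test), close to the stated 665.
- All 665 followed for 12 weeks after their last dose: 665 × 8/52.18 = 102 subject-years per arm. This is an upper bound for the mandated window.
- 70% followed, using the planned dropout as a stand-in: 0.7 × 665 × 8/52.18 = 71 subject-years per arm.

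**Events in the gap, at assumed rates** (the protocol gives none)

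| Assumed rate per 100 subject-years | 71 subject-years | 102 subject-years |
|---|---|---|
| SAEs, 5 | 3.6 | 5.1 |
| SAEs, 10 | 7.1 | 10.2 |
| SAEs, 15 | 10.7 | 15.3 |
| Deaths, 0.5 | 0.4 | 0.5 |
| Deaths, 1 | 0.7 | 1.0 |
| Deaths, 2 | 1.4 | 2.0 |

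That is about 4 to 15 SAEs and about 0.4 to 2 deaths per arm. The death row overstates the omission somewhat, because an AE that starts inside the 4-week window and proves fatal later is still counted.

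**The case against.** The best defence is that nothing is lost. TEAE tables are the right main safety display, off-drug events dilute drug-related differences, and every SAE and fatal AE is listed. On this view, what remains is a wish for two extra tables, and tables are usually chosen in the SAP. The first part stands and keeps the point minor. The second does not: the protocol did not leave the choice open but wrote a rule that excludes these events.

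Several stronger readings are tempting, and the documents do not support them.
- **That harm is tabulated for a shorter time than the primary benefit.** For completers, the primary comparison is at week 104 and the TEAE window runs to week 108, so it is covered. Only the 27-month secondary endpoint reaches week 116, and under 9.7.1.6.2 it is tested only after the primary and every higher-ranked test succeed. An on-treatment safety window beside an analysis that ignores adherence answers a different question; it is not a contradiction.
- **That far more follow-up is omitted.** Suppose 30% stop drug evenly over 104 weeks and all return to month 24. Their mean time outside the tables is then (4968 + 96)/104 = 48.7 weeks, and 0.7 × 8 + 0.3 × 48.7 = 20.2 weeks per subject gives about 257 subject-years per arm. But this brings back to month 24 the same subjects that 9.7.2 counts as dropouts. It also uses time beyond 12 weeks off drug, when SAE collection is not mandated and AEs are only asked about at two visits.
- **That the SAP could not even count deaths.** The rule concerns which AEs enter AE tables. It does not clearly forbid a plain count of deaths by arm.
- **That late lymphocytopenia disappears.** The by-visit laboratory summaries show it.

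**Conclusion.** The point holds in a limited form. For SAEs and fatal AEs with onset 4 to 12 weeks after the last dose, the protocol mandates collection and then excludes them from every by-arm SAE and fatal-AE table. The 8-of-12-week gap follows from the text alone. Its person-time is at most about 102 subject-years per arm, resting on complete follow-up of 665, and about 71 if 70% are followed. Event counts rest wholly on assumed rates, and the direction of any arm difference in the omitted events is unknown.

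A reader might infer that safety reporting is biased or that the benefit-risk comparison is invalid. Neither follows: the events are listed, and the primary period is covered. This is a cheap improvement. Only part of the document is at hand, so a version not shown may already read differently; the wording is the same in both statistical sections that are shown.

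**What to change.** In section 9.7.1.8.2, replace the restricting sentence with: *AE summary tables are based on TEAEs, except that all deaths and all SAEs with onset after the first dose and through 12 weeks after the last dose will also be summarized by treatment group; events recorded later in subjects who stopped study drug early will be shown separately.* In the sentence on fatal events, report TEAEs leading to death as a subset of all deaths.

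The cost is one changed sentence, a matching edit to the death sentence, and two tables from data already collected. The downside is that off-drug events dilute drug-related differences, and capture beyond 12 weeks depends on who returns. The TEAE tables should therefore remain the main display, with the added tables labelled supplementary.

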9.7.1.8.3 LABORATORY VALUES

Laboratory results will be summarized using International System of Units, as appropriate. For all quantitative parameters listed in [Section 9.5.1.5.3](#), the actual value and the change from baseline to each postbaseline visit and to the end of treatment (defined as the last on-treatment value) will be summarized by visit and treatment group using descriptive statistics. Qualitative parameters listed in [Section 9.5.1.5.3](#) will be summarized using frequencies (number and percentage of subjects), and changes from baseline to each postbaseline visit and to end of treatment will be reported using shift tables. Percentages will be based on the number of subjects with both nonmissing baseline and relevant postbaseline results.

Laboratory test results will be assigned a low/normal/high (LNH) classification according to whether the value was below (L), within (N), or above (H) the laboratory parameter's reference range. Within-treatment comparisons for each laboratory parameter will be based on 3-by-3 tables (shift tables) that compare the baseline LNH classification to the LNH classification at each postbaseline visit and at the end of treatment. Similar shift tables will also compare the baseline LNH classification to the LNH classification for the highest and lowest value during the treatment period.

[Appendix 1](#) (Sponsor's Grading for Laboratory Values) presents the criteria that will be used to identify subjects with treatment-emergent markedly abnormal laboratory values (TEMAVs). Except for phosphate, a TEMAV is defined as a postbaseline value with an increase from baseline to a Grade of 2 or higher. For phosphate, a TEMAV was defined as a postbaseline value with an increase from baseline to a Grade of 3 or higher. When displaying the incidence of TEMAVs, each subject may be counted once in the laboratory parameter high and in the laboratory parameter low categories, as applicable.

9.7.1.8.4 VITAL SIGNS

Descriptive statistics for vital signs parameters (ie, systolic and diastolic BP, pulse, respiratory rate, temperature, weight), and changes from baseline will be presented by visit and treatment group.

9.7.1.8.5 OTHER SAFETY ANALYSES

Cognitive decline will be assessed as a safety assessment, in addition to efficacy assessments. Cognitive assessments will include the ADAS-cog₁₄, MMSE, and CDR. (see [Section 9.7.1.6](#)).

vMRI will be used to evaluate disease modification as indicated by measurements of brain atrophy, including the change from Baseline in terms of the measured hippocampal volume based upon the centralized measurement of the structure on repeated MRIs. A large number of studies, including the AD Neuroimaging Initiative, have shown that quantitative measurements of hippocampal, whole brain, and total ventricular volume provide robust and reliable biomarkers of disease progression, and potential for assessment of PD efficacy.

MRI sequences will be collected for all subjects at 12 and 24 months per the Schedule of Assessments. vMRI data will be analyzed at the Screening Visit and at Visits 9 and 13 (12 and 24 months of treatment). QC and normalization procedures for measurements of the whole brain, total ventricular volume, and right and left hippocampal volumes will be based on a validated algorithm and conducted in the same central laboratory. Additional analysis of regions of interest and cortical thickness may also be performed.

9.7.2 Determination of Sample Size

The sample size for this study is estimated based on comparison of elenbecestat (E2609) versus placebo with respect to the primary efficacy endpoint, the change from baseline CDR-SB at 24 months. Based on available ADNI data [amyloid positive, MMSE equal or greater than 24, late MCI (global CDR=0.5) populations from ADNI, ADNI 2 and ADNI GO] the mean and the standard deviation of the change from baseline in the CDR-SB at 24 months in the placebo group are assumed to be 1.75 and 2.05, respectively. Therefore, assuming a 25% reduction in the mean change from baseline CDR-SB at 24 months for the elenbecestat (E2609) 50 mg per day dose group compared to placebo with a common standard deviation of 2.05 and an estimated 30% dropout rate in this study, a total sample size of 1330 subjects, 665 subjects in each treatment group, will be required to detect the treatment difference between elenbecestat (E2609) 50 mg per day and placebo using a 2-sample t-test with 90% power at a significance level of 2-sided alpha =0.05.

9.7.3 Interim Analysis

This is a fixed design. There is no interim analysis of efficacy and no alpha spending before final analysis. However, a futility analysis is planned when 30% subjects have completed 24 months. The sponsor may stop the trial for futility with nonbinding futility boundary calculated using conservative O'Brien-Fleming boundary of Lan-DeMets alpha spending function with 30% information based on completers. If the actual percent information of the futility analysis is different from 30%, the futility boundary will be recalculated using the actual percent information at time of futility analysis. A blinded sample size re-estimation through estimated standard deviation based on blinded data prior to the completion of enrollment, will be performed if there is an indication that sample size assumptions need to

be changed. This blinded sample size re-estimation could be performed based on signals from external studies or based on review of blinded data from this study prior to completion of enrollment. The standard deviation of the primary endpoint was estimated based on data from the ADNI study. It is possible that the standard deviation for the same endpoint in clinical trials may be larger than that from this observation study.

An independent DSMB will convene at regular intervals to monitor the overall safety of the study and to make recommendations to the sponsor related to study safety as appropriate. The DSMB will be asked to review the cumulative safety data up to the date identified to make a determination if the trial is safe to proceed unchanged or to provide recommendations to the Sponsor as to how to proceed. The study will proceed, including randomization of additional subjects, during DSMB safety reviews. DSMB reviews will then continue to occur at regular intervals. Details will be provided in the DSMB Charter.

